### **3.4 Additional Safety Endpoints**

- Adverse events (spontaneously reported)

- Physical examination
- Vital signs
- 12-lead electrocardiograms
- Clinical laboratory parameters
- C-SSRS

**3.5 Resource utilization:**

- Any CV events and/or related resource utilization such as visits to cardiologists, procedures, hospitalizations, new treatments or treatment adjustments for CV disease on study **Visit 1** through **Visit 6/EoS/ET**.
- Any visits to an emergency room or physician’s office for treatment of migraine on study **Visit 1** through **Visit 6/EoS/ET** excluding study specific visits.
- Concomitant medications for the treatment of migraine and/or pain **Visit 1** through **Visit 6/EoS/ET**.
- Missed days of work and/or school or daily activities based on responses to MIDAS questionnaire.
- MIDAS Total score.

**4 ANALYSIS POPULATIONS**

The following analysis populations will be defined for this study.

#### 4.1 Examination of Subgroups

Subgroup analyses will be performed for subjects with one or more cardiovascular risk factors. Similar criteria as parent study will be used to identify the subjects with one or more cardiovascular risk factors. It should be noted that the parent or current study was not designed to detect treatment differences with high statistical power within subgroups.

- Cardiovascular Disease Risk Factors
  - Hypertension
  - Hypercholesterolemia
  - Smoking
  - Obesity
  - Diabetes Mellitus
  - Strong family history of coronary artery disease
  - Males over 40 years
  - Post-menopausal females

## 5 GENERAL SPECIFICATIONS

This section details the specifications for summarizing all efficacy and safety endpoints.

All safety analyses will be based on the safety population. Efficacy analyses will be performed on ITT population, with the exception of the MBS-free and headache pain-free analyses secondary endpoint which will be performed on the mITT population.

Continuous variables will be summarized using descriptive statistics, i.e. n (number of subjects with available data), mean, median, standard deviation (SD), minimum, and maximum. For those measures that are analyzed using change from baseline scores, descriptive statistics will also be presented on observed scores, unless otherwise noted.

Minimum and maximum values will be presented to the same precision as the raw data. Mean and median will be presented to one more decimal place than the raw data. Standard deviation will be presented to two more decimal places than the raw data.

Categorical variables will be summarized using counts and percentages. Unless otherwise specified, percentages will be calculated using the numbers of subjects in the summarized population in each treatment group as denominators. Percentages will be presented with a precision of 1 digit after the decimal.

In this study, subject will enter the efficacy data on dosing and post-dose assessments in an e-diary. The e-diary records the date and time of the first dose and of the second dose and is programmed to assess specific time points and assessments as defined in the protocol based on the timing of the dose as recorded. This data is collected in the e-diary when e-diary is in migraine mode. Subjects will record the dosing information for every migraine attack in this study. Specifics of Migraine Mode are as below:

- Migraine Mode – First Dose
  - The e-diary enters Migraine Mode **ONLY** if the subject indicates taking his/her first dose of study medication
  - Post Dose Assessments will be completed using the Migraine Questions button at specific time intervals for up to 48 hours after the subject confirms taking study medication
    - The time intervals are 30 minutes, 1 hour, 2 hours, 4 hours, 24 hours, and 48 hours after the first dose of study medication. The e-diary sets the post dose assessments based on the recorded time of dosing. A subject that begins reporting their migraine at the exact time of dosing will have all of the post dose assessment time points available to them. If a subject starts recording their information in the e-diary after they dose including the

time of dosing, the assessments that become available for them are based on the time of dosing, relative to when they accessed the e-diary. For example, if at 1-hour post actual dosing the subject initiates migraine mode and begins entering data into the e-diary, the subject will be allowed to respond to the initial questions about their migraine and time of dosing and then based on the time they record for dosing they automatically will miss subsequent time points, i.e.; the 30 minute and 1-hour time points.

- Alarms occur at the predefined time points to remind the subject it is time to complete the assessments. The Migraine Questions button is always available, but the subject is not able to answer the questions until the assessment time (+/- 5 minutes or +/- 10 minutes depending on the time point).
- Migraine Mode – Second Dose (Optional)
  - The subject should only take a second dose of study medication if the migraine pain is not gone by two hours after the first dose or the migraine pain was gone and came back two hours or more after the first dose (up to 24 hours after first dose).
  - The Dose 2 button will appear AFTER the e-diary recognizes 2 hours have passed since the first dose and remains until the 24-hour time point.
  - During the 2-hour post dose assessment the subject will be asked to indicate if he/she would like to take a second dose of study medication
  - If a second dose is reported alarm intervals are the same as for the reporting of the first dose and any remaining alarms from the first dose are cancelled. However, if the subject inadvertently enters a dosing time of the second dose occurring prior to the first dose, the first dose alarms do not stop and subject can therefore respond to post-dose assessments based on time of dosing of first dose.

In the event that e-diary dates and times are not entered by subject as described in specifics of Migraine Mode but subject actually takes a dose, the dates of dosing based on subject report will be recorded in the case report form (CRF) at the site. Subject will be asked about their dosing and any unusual symptoms they experienced with their migraine that they had not experienced before. To make the use of CRF date entry consistent across all subjects, these CRF dates and times data will be completed for all subjects even if subject has entered the dates and times on e-diary. This may cause more validation for efficacy and safety analysis dates will be further described in detail in below sections.

Observations collected prior to first dose will serve to determine a baseline measurement; the latest available measurement prior to first dose will be used as the baseline. For safety purposes, the first recorded date and time at which a dose was taken will be used for baseline, without regard for the source of that date (e-diary or CRF) for each treated migraine attack. For efficacy purposes,

baseline values will be the Hour-0 assessment times identified in the e-diary for each treated migraine attack. Analyses of efficacy data collected after the second dose may require a second “Hour-0” defined by the e-diary relative to the entered time of that second dose for each treated migraine attack.

Safety Analysis: Below assumptions will be considered for determining the start and end dates for treatment exposure.

1. If CRF dates data is matched with e-diary dates and times: The start and end of treatment exposure for analysis will always be identified from the first and last dates of dosing entered in the CRF, when available and appear to match the e-diary dosing data.
2. If CRF dates data is NOT matched with e-diary dates: CRF dates will be compared with e-diary dates and times for possible and reasonable match. If CRF dates appear to be out of order i.e. second dose date and/or time recorded in e-diary is before first dose date and/or time; same first and second dose dates and time in e-diary, such dates and/or time will not be corrected by CRF data as provided by the subject due to unavailability of times of dosing in CRF. In such cases, if the CRF dates and e-diary dates do not match, then for overall treatment exposure, earliest date available from CRF or e-diary will be considered for start of exposure and latest date available from CRF or e-diary will be considered for end of exposure. Additionally, for first dose exposure, earliest date available from CRF or e-diary will be considered for start of exposure of first dose and latest date will be considered for end of exposure of first dose. Similarly, for second dose exposure, earliest date available from CRF or e-diary will be considered for start of exposure of second dose and latest date will be considered for end of exposure of second dose.
3. If CRF dosing dates are available but e-diary dosing information is missing: CRF dosing date will be determined as confirmation of dosing at sites even if subject could not enter dosing information in e-diary due to any reason. These subjects data will be used for analysis. If the first dose date is available in CRF but missing from e-diary then eligibility date will be used as the first alternative and the randomization date will be used as second alternative. If the second dose date is available in CRF but missing from e-diary then study completion/discontinuation date will be used as the alternative. Additionally, for CRF dosing dates which are partial dates, missing dates and dates which fall outside the visit window, reported visits windows with respect to reported CRF dosing dates windows will be used for treatment start and end dates.

4. If CRF dosing dates are NOT available but e-diary dosing information is available: It will be determined that these subjects have not confirmed this dosing at the site (or are lost to follow-up) and there is no confirmation on exact dosing on CRF. These unconfirmed migraines will be excluded from safety analyses.

The statistical evaluation will be performed using SAS version 9.4 or higher.

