## **6 DISPOSITION OF SUBJECTS AND DISCONTINUATIONS**

The following will be summarized for all subjects by treatment arm, as counts and percentages of all subjects. Disposition data will be also presented for Safety Population and Pre-administrative Hold Population Subjects.

- Subjects randomized
- Subjects with confirmed eligibility
- Subjects treated with second dose
  - For Rescue and with Recurrence
- Overall number of attacks treated
  - Number of attacks treated with 1 dose
  - Number of attacks treated with 2 doses
- Average number of attacks treated in a 30 day period over participation in the study.
- Subjects in each of the analysis populations:
  - Randomized population
  - ITT population
  - ITT 2nd Dose Population
    - Rescue Population
    - Recurrence Population
  - mITT population
  - Safety population
  - 3-Month Safety Population
  - 6-Month Safety Population

- 12-Month Safety Population
- Duration of time in study for Safety, 6-Month Safety and 12- Month Safety Population (Mean, Median, 25th Quartile, 75th Quartile, SD, Minimum and Maximum)
- Subjects who completed the study for 12 month
  - Treated
  - Not treated
- Discontinued subjects before 12 months
  - Treated
  - Not treated
- Reasons for subject discontinuation
  - Adverse event
  - Death
  - Lost to follow-up
  - Non-compliance with protocol requirements
  - Pregnancy
  - Subject request
  - Investigator request
  - Sponsor request
  - Missing
- Discontinuations within 48 hours of last dose, by reason for discontinuation.

The number and percentage of subjects in each disposition category will be presented; percentages will be based on the number of all subjects. Percentages for the number of subjects randomized will be based on the total number of subjects who enrolled in the study. Percentages for the treated status of discontinued subjects will be based on the number of subjects who discontinued. For discontinuation reasons, percentages will be based on the number of subjects who discontinued. Subjects' inclusion in the analysis populations will be listed. Disposition data and all subjects who discontinue from the study will be presented in a separate listing.

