### **12.1 Adverse Events**

An AE with the date of onset on or within 48 hours after a dose of study drug, or an event that worsens in intensity within 48 hours of a dose of study drug will be considered a treatment-emergent adverse event (TEAE). Other AEs are defined as those occurring after randomization but not considered to be treatment-emergent.

Descriptive statistics for both number of subjects ever experiencing an event as well as for the total number of events will be presented. Furthermore, descriptive statistics will also be calculated for each treatment group irrespective of first or second dose for AE relationship and AE severity. If multiple intensities are reported for a given AE and subject, then the most severe intensity will be counted. A separate, similar analysis will be conducted for TEAEs.

AEs with a missing start date will be assumed to be treatment-emergent, except in situations described in Appendix 1. If a subject takes at least one dose of study drug, but the date and time of dosing is missing in the e-diary, all AEs for that subject will be considered treatment-emergent, if the AEs occur between available date of dosing as recorded only in CRF for up to 48 hours (2 days) post recorded date of dosing. If the date and time of the second dose is missing in e-diary then all AEs for that subject will be considered as treatment emergent due to second dose, if AEs occur between available date of dosing in CRF for second dose, and an ending boundary of 2 days after recorded date of dosing with second dose, inclusive. See Appendix 1 for derivations related to partial dates and times.

Nausea and/or vomiting reported as adverse events during a migraine by any subject that also noted these as characteristics of their migraine will be presented by treatment groups and not be considered related to treatment but rather an underlying condition of the migraine.

AEs will be coded by the Medical Dictionary for Regulatory Activities (MedDRA) version 21.0.

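### SAP Section 5, Safety Analysis item 3, sets exposure start and end from administrative dates when the CRF already holds the dose date

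*SAP*

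**What the plan says.** SAP Section 5 introduces four Safety Analysis rules with "Below assumptions will be considered for determining the start and end dates for treatment exposure". Item 3 deals with dosing that is on the CRF but absent from the e-diary. It keeps these subjects in the analysis, because the "CRF dosing date will be determined as confirmation of dosing at sites". It then assigns dates:

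- First dose: "If the first dose date is available in CRF but missing from e-diary then eligibility date will be used as the first alternative", with the randomization date as second choice.
- Second dose: "If the second dose date is available in CRF but missing from e-diary then study completion/discontinuation date will be used as the alternative".

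A further sentence in item 3 sends CRF dates that are partial, missing or outside the visit window to a visit-window rule.

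Other parts of the SAP use the CRF date itself. For the safety baseline, "the first recorded date and time at which a dose was taken will be used for baseline, without regard for the source of that date". In SAP 12.1, when the e-diary dosing time is missing, adverse events count as treatment-emergent "if the AEs occur between available date of dosing as recorded only in CRF" and up to 48 hours afterwards, with a parallel sentence for second doses.

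**The concern.** Item 3 accepts the CRF entry as proof that the dose was taken, then names a different date for it. Neither substitute is a dosing date. Eligibility is settled at Visit 1 before drug is dispensed, and the completion or discontinuation date marks study exit. Exposure would therefore start too early or end too late in a study whose primary objective is long-term safety. The same dose could also carry one date for exposure and another for adverse-event emergence. Displays that depend on the earliest or latest dose would inherit the error if they are built from these dates.

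**Working it through.** **Step 1. Which dates does item 3 replace?** The condition in both substitution sentences is that the date is available in the CRF. Unusable CRF dates have their own sentence. On plain reading, the substitution therefore applies to CRF dates that are known.

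**Step 2. How do the other rules treat a CRF date?**

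| Rule | Situation | Date used |
|---|---|---|
| SAP 5, item 1 | CRF and e-diary agree | CRF date |
| SAP 5, item 2 | CRF and e-diary disagree | earliest and latest from either source |
| SAP 5, item 3 | CRF present, e-diary missing | eligibility or randomization; completion or discontinuation |
| SAP 5, safety baseline | any | first recorded dose, either source |
| SAP 12.1 | e-diary dose time missing | CRF date plus 48 hours (2 days) |

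Only item 3 sets a usable CRF date aside.

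**Step 3. How far off are the substitutes?** The SAP gives no figure to reproduce, so the size comes from the visit schedule.

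- Nominal Visit 6 (Protocol 5.4.1): 30 + 60 + 90 + 90 + 90 = Day 360.
- Summed visit windows: 2 + 4 + 4 + 4 + 4 = 18, so Day 342 to Day 378. The upper end agrees with the stated maximum of 54 × 7 = 378 days.
- Protocol 8.5 has subjects screened outside an attack, so eligibility (taken as Day 0) is expected to precede the first dose.
- Protocol 5.4.1 puts the end-of-study visit 7 ± 2 days after the last treated migraine. The shortest per-schedule gap is 7 − 2 = 5 days (Protocol 5.5.5 says at least 7). That is 5 − 2 = 3 days beyond a 48-hour window. An early-termination visit can fall closer to the last dose.

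Take an attack whose two doses are dated Day D on the CRF and are both missing from the e-diary, in a subject who completes on Day 360:

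- first-dose shift = D − 0 days too early;
- second-dose shift = 360 − D days too late;
- apparent separation of the two doses = D + (360 − D) = 360 days, against a permitted maximum of 24 hours.

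| D | First dose too early by | Second dose too late by |
|---|---|---|
| 30 | 30 days | 330 days |
| 180 | 180 days | 180 days |
| 350 | 350 days | 10 days |

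If the CRF date were used, both shifts would be 0.

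**Step 4. What follows if other displays use these dates?** Both cases below are conditional, because the SAP names no source for the dose date in either place.

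- SAP 6 lists "Discontinuations within 48 hours of last dose, by reason for discontinuation". Take a subject whose last dose is a second dose on CRF Day 40 and who discontinues on Day 200. The true gap is 200 − 40 = 160 days. Under item 3 it is 200 − 200 = 0 days, and the subject enters the table.
- Appendix 16.1 calls a medication concomitant if it starts no later than the latest dose plus 2 days and stops no earlier than the earliest dose. For the same subject the start limit moves from Day 40 + 2 = 42 to Day 200 + 2 = 202, so a medication started from Day 43 onwards changes from post-dose only to concomitant. Likewise, if a true first dose on Day 30 is re-dated to Day 0, a medication stopped between Day 0 and Day 29 changes from prior only to concomitant.

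**The case against.** The strongest reply concerns scope. The lead-in confines items 1 to 4 to exposure start and end. A reader might infer that treatment-emergent event counts, and so the primary endpoint, rest on false dates. The documents do not support that: SAP 12.1 uses the CRF date for this very case, for first and second doses, and the safety baseline accepts either source. Appendix 16.2 refers to a dose date/time without naming its source, but that silence does not override SAP 12.1. This part of the reply stands.

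A reader might also infer that affected subjects are automatically counted as discontinuing within 48 hours of last dose. SAP 6 does not say that last dose comes from item 3, and a subject leaving at the scheduled Day 360 visit is a completer, not a discontinuation. Appendix 16.1 is equally silent on its source, and SAP 9 plans no separate table of post-dose medication. These effects can only be stated conditionally.

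Much of the exposure reporting in SAP 10 consists of counts of subjects, doses and attacks, and the 3-, 6- and 12-month safety populations rest on participation time and attack counts. The exit-date error therefore does not by itself change who belongs to those populations. That also stands.

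Finally, the word alternative may signal a fallback meant for dates missing from both sources. That may be the intent, but the text states the opposite condition and handles unusable CRF dates separately. If a fallback was meant, the rule is miswritten and still needs correction. Items 2 and 3 cover different situations, so they differ in logic rather than contradict each other outright.

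**Conclusion.** The point holds for exposure start and end dates. As written, item 3 replaces a known CRF dose date with one that is expected to be too early (first dose) or, for a per-schedule completer, is at least 5 days too late (second dose). In the extreme, the two doses of one attack lie about 360 days apart. This is out of line with items 1 and 2, the safety baseline rule and SAP 12.1.

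No effect on treatment-emergent status or safety baseline is shown. Effects on the 48-hour discontinuation table and on medication classes depend on an unstated link to item 3. The day counts assume eligibility on Day 0 and completion on Day 360; the Day 40 and Day 200 case is constructed. The documents do not say how many doses are affected, so the effect on any reported result cannot be sized, although SAP 5 and 5.7 treat missing e-diary dosing as a situation to plan for.

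**What to change.** Rewrite item 3 as follows:

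1. When the CRF dose date is known and the e-diary entry is missing, use the CRF date for exposure start and end, for first and second doses alike.
2. Delete the eligibility, randomization and completion/discontinuation substitutions for known CRF dates.
3. Keep the existing visit-window rule for CRF dates that are partial, missing or out of window.
4. State that the same CRF-based dose date feeds the 48-hour discontinuation table in SAP 6 and Appendices 16.1 and 16.2, consistent with SAP 12.1.

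The cost is a change of SAP wording and one derivation. No new data are needed, since the CRF dates are already collected.

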### **5.1 Changes and Clarifications from the Planned Analysis**

The protocol detailed mITT-2nd Dose and PP-2nd Dose populations. However, the decision was made to run efficacy analyses on the ITT and mITT populations. The populations such as safety-2nd, mITT-2nd Dose and PP-2nd Dose populations were therefore removed. Additionally PP population was removed, as primary endpoint of this study is safety.

The analyses of the primary efficacy measure and other related measures described in the protocol were limited to headaches that were of moderate or severe intensity at the time of dosing. In keeping with subsequent input to CoLucid from the Food & Drug Administration (FDA), the efficacy endpoints will take into account headaches that were of mild intensity at the time of treatment.

The protocol mentioned sensitivity analysis for efficacy endpoints for missing diary data. It was decided not to conduct this analysis, as primary endpoint of this study is safety. The complications of missing efficacy diary data were tested in parent study.

The protocol does not mention an additional subgroup analysis but subgroup analyses described in Section 11.8 will be provided.

Though the protocol did not specify this, it was decided that exploratory analyses would be repeated separately for relief of each associated symptom of headache, including vomiting.

